7. GENERAL OBJECTIVE

To determine the effect of the use of a nutritional support system on complications in patients with COVID-19 and comorbidities (type 2 DM, HAS, overweight/obesity with BMI <35) in stage III, compared with conventional nutritional treatment.

7.1. SPECIFIC OBJECTIVES

1. To correlate biochemical and inflammatory factors with the evolution of the study groups.
2. To correlate body composition with the clinical evolution of the patients.
3. To evaluate the days of hospital stay, disease progression, percentage of progression to ventilator and mortality as predictive indexes of patient improvement.
4. To stratify in groups by age ranges (30-39, 40-49, 50-59 and >60 years).

8. METHODOLOGY

8.1 Type of study and overall design: Blinded, randomized controlled clinical trial.

8.2 Study Universe.

Patients diagnosed with COVID-19 by PCR test, who are attended at Centro Medico ISSEMYM Toluca Arturo Montiel Rojas, located at [name]; both sexes, with presence of comorbidities and in stage III.

8.3 Selection and sample size: the sample size will be calculated using the formula: $n = \frac{z^2 pq}{e^2}$, where: 95% confidence level ($z = 1.96$), $p = 0.975$, $q = 0.025$, with a margin of error of 5% ($e = 0.05$), obtaining 38 patients per group for the sample.

8.4 Inclusion and exclusion criteria

Inclusion criteria: 1. Patients admitted to the Centro Medico ISSEMYM Toluca Arturo Montiel Rojas, diagnosed with COVID-19. 2. Patients in need of supplemental O₂ with nasal prongs or mask-reservoir due to satO₂ <90% and respiratory distress. 3. With concomitant diseases such as cardiovascular disease, diabetes mellitus 2, hypertension, overweight or obesity BMI <35. 4. 5. Over 30 years of age. 6. Tolerant of oral feeding. 7. Signed informed consent letter.

Non-inclusion criteria: 1. Who requires mechanical ventilatory support. 2. 2. Present neurological or neurodevelopmental disorders. Severe gastroesophageal reflux and/or dysphagia. 4. 4. Patients with any type of surgery performed in a period of less than 3 months. 5. Allergies to any ingredient of the study treatment. 6. Who present acute malnutrition. 7. Patients who require admission to the Intensive Care Unit. 8. Who has criteria of sepsis or septic shock. 9. Glomerular filtration rate less than 60ml/min/1.73m².

Criteria for elimination: 1. Treatment failure. 2. Admission to ICU for any reason. 3. Patients who do not tolerate the oral route. 4. Reactions to treatment that compromise the health of the patients.

Sampling and allocation: Consecutive cases. Systematic randomized allocation by means of a sequence of random numbers constructed with the Excel program divided into two groups.

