The energy balance of the supplements will be considered within the designated caloric balance for this group. The follow-up will be performed daily for 21 days or earlier, if they are discharged from hospital due to improvement in evolution or require access to the ICU, at which time the patient concludes the study. The following points will be supervised: 1. Application and consumption of the NSS supplementation as appropriate. 2. Recording of all the information in the records. 3. Food diaries of each patient. 4. Laboratory studies: QS every other day, BH every 3rd day, coagulation times every 3rd day, D-dimer and fibrinogen every 3rd day, serum electrolytes every other day, serum homocysteine every other day and serum 25 hydroxycholecalciferol levels every other day. 5. SpO2 %, heart rate, respiratory rate. 6. Clinical evaluation and record of bowel movements. 7. Taking of tricipital fold and arm

circumference, % muscle mass, % fat, BMI, weight, height every two days. 8. Days of hospital stay.

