Item 13b: Any planned adjustment of the significance level due to interim analysis:

No adjustment of the significant level due to interim analysis are planned.

13c. Details of guidelines for stopping a trial early:

The following points are considered in planning the early stopping of the study:

1. That the intervention causes serious adverse effects in patients generating insecurity in its application.
2. That the investigators detect improbable, ineffective, or extreme differences between the CG and the IG.

3. New information emerges that raises serious safety issues or convincingly answers to the main question.

14. Timing of final analysis

Item 14: Timing of final analysis e.g all outcome analyzed collectively or timing stratified by planned length of follow-up

The follow-up will start in September 2020 until the established sample is met.

The last day of the study for each patient is going to be 40 days after hospital discharge.

Statistical analysis of clinical and biochemical variables will be performed on baseline, day three, hospital discharge and day 40. Analysis of overall survival and mortality will be performed from baseline to day 40 or patient death. Progression of patients to Mechanical Ventilation Assistance (MVA) will be performed from baseline until the last patient is intubated, mortality in patients with MVA will be performed from intubation to day 40 or death.

15. Timing of outcome assessments

Item 15: Time points at which the outcomes are measured

Survival and Mortality

- Overall survival and mortality: performed from baseline to day 40 or patient death.
- Progression of patients to Mechanical Ventilation Assistance (MVA): performed from baseline until the last patient is intubated.
- Mortality in patients with MVA: performed from intubation to day 40 or death.

Clinical and biochemical variables

- Delivered oxygen flow and maintenance of SpO₂ > 90%: will be analyzed at baseline and day three.
- qSOFA scale: will be analyzed at baseline compared with day three.

- Gastrointestinal function (average of gastrointestinal movements, abdominal distension, and Bristol scale): will be analyzed at baseline compared with day three.
- Laboratory parameters: will be analyzed at baseline, day three and hospital discharge.
- PHQ-9: will be analyzed at baseline and hospital discharge.

Follow-up at day 40

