- Not meeting inclusion criteria including patients with respiratory rate disturbance (>30 bpm), glycemia >250 mg/dl, Glomerular filtration rate (GFR) < 60 ml/kg/m², platelets level (<150 10³ /L), concomitant autoimmune diseases (hypothyroidism, rheumatoid arthritis, atopic dermatitis), and/or respiratory disorders (bronchial asthma, obstructive sleep apnea syndrome, chronic lung lesions).
- Declined to participate.
- Randomization of all patients.
- Assignment of 40 patients to CG (received hospital diet and hospital treatment) and 40 patients to IG (received intervention - NSS, probiotics, B complex, hospital diet, and hospital treatment).

- Report of incidents.
- Variables analyzed in both groups with their evaluation periods.
- Primary outcomes.

24. Withdrawal/ Follow-up - level of withdrawal

Item 24a: Level of withdrawal e.g. from intervention and/or from follow up

The withdrawal levels that could be present in the study are listed as follows:

1. Participants can withdraw from the intervention and follow-up stops but the information collected is considered as data.
2. If patients decide to withdraw from follow-up, they are asked to allow us to use the data collected to date.
3. If a patient does not allow his/her data to be analyzed, they will not be considered in the analysis.
4. If the patient presents secondary reactions or does not adequately follow the treatment, they should leave the study and their data will be considered for the analysis.
5. Data from patients who die will be considered in the analysis.

Item 24b: Timing of withdrawal/lost to follow up data

The report of withdrawals and losses will be established in the CONSORT diagram, Kaplan-Meier curves, and primary outcomes section, where the timing of withdrawals will be mentioned, as well as the analysis and number of deaths.

Item 24c: Reasons and details of how withdrawal/lost to follow up data will be presented

Reasons for patients deciding to withdraw and deaths from COVID-19 complications will be presented on the CONSORT diagram, Kaplan-Meier curves, and in the primary outcomes section.

25. Baseline patient characteristics

Item 25a: List of baseline characteristics to be summarized

The clinical characteristics, demographic analysis and baseline values will be presented in tables. Details of the randomization will be mentioned in the methods section.

Item 25b: Details of how baseline characteristics will be descriptively summarized

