Categorical data will be summarized by numbers and percentages. Normality tests will be applied to evaluate the distribution of the data. If the continuous data present a normal distribution, they will be assumed by mean, SD, and range. If they do not present a normal distribution, they will be summarized with the median and the IQR. Minimum and maximum values will also be presented for continuous data. Statistical significance tests will be performed between both groups in the baseline to rule out significant differences.

Section 6: Analysis

26. Outcomes definitions

Item 26a: Specification of outcomes and timings

Primary outcomes

- Overall mortality and survival will be assessed from the baseline to day 40.
- Progression to AVM will be assessed from baseline until the last patient is intubated.
- Mortality and survival in intubated patients will be assessed from baseline to day 40.

These results will be included in the results section of the manuscript.

Secondary Outcomes

Administration of supplemental oxygen flow, oxygen saturation (spO₂), qSOFA scale, and gastrointestinal function will be assessed by comparing at baseline to day 3 intragroup and intergroup. The PHQ-9 test will be assessed at baseline and at discharge between both groups.

These results will be included in the secondary outcomes section of the manuscript. Analysis of the association of baseline biochemical parameters and mortality will be considered in a table and in the secondary outcomes section of the manuscript.

The spO₂ without supplemental oxygen requirement, home supplemental oxygen requirement, post COVID syndrome, and body weight at day 40 will be analyzed between both groups in a table.

These results are included in the follow-up section of the manuscript.

Item 26b: Specific measurement and units

- SpO₂ (%)
- Mortality (days of death)
- Kilocalories (kcal / day)
- PHQ9 (pts).
- Temperature (°C).
- Hemoglobin (g / dL).
- Mean corpuscular volume (fL).
- Mean corpuscular hemoglobin concentration (g / dL).
- Leukocytes ($10^3 / \mu\text{L}$).
- Neutrophils (%).
- Platelets ($10^3 / \mu\text{L}$).
- Glucose (mg / dL).
- Total cholesterol (mg / dL).
- Triglycerides (mg / dL).
- Aspartate aminotransferase (U / L).
- Alanine aminotransferase (U / L).
- Albumin (g/dL).
- Blood Urea Nitrogen (mg / dL).
- Urea (mg / dL).
- Creatinine (mg / dL).
- Glomerular filtration rate
- Ferritin (ng / mL)
- Fibrinogen (mg / dL)
- C-reactive protein (mg / L)
- Dimer-D (ng / mL)

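### The protocol ends follow-up at ICU need, discharge or day 21, but the SAP's primary outcomes need vital status to day 40, and SAP Item 24a stops follow-up of patients who leave

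*Protocol*

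**What the plan says.** **Protocol.** Section 8.4 (inclusion and exclusion criteria) sets "Criteria for elimination: 1. Treatment failure. 2. Admission to ICU for any reason", and adds oral intolerance and health-compromising reactions. Section 8.4 (procedure) states: "The follow-up will be performed daily for 21 days or earlier". The earlier ends are discharge for improvement, or that patients "require access to the ICU, at which time the patient concludes the study".

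**SAP outcomes.** Item 15 has "Overall survival and mortality: performed from baseline to day 40 or patient death". Item 26a lists three primary outcomes: overall mortality and survival, progression to mechanical ventilation, and mortality and survival of intubated patients. The start for the last is given in two ways. Item 15 has "Mortality in patients with MVA: performed from intubation to day 40 or death", while Item 26a has "Mortality and survival in intubated patients will be assessed from baseline to day 40". Item 14 places each patient's last study day 40 days after discharge.

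**SAP leavers.** Item 24a point 1 reads "Participants can withdraw from the intervention and follow-up stops", with the data gathered so far retained. Point 4 reads "If the patient presents secondary reactions or does not adequately follow the treatment, they should leave the study", again retaining data. Point 5 includes patients who die, but no point provides for learning vital status after exit. Item 28 plans no missing-data method. Item 20 has both groups, 80 patients in all, analysed, without saying that each is analysed in the arm assigned.

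**The concern.** The primary endpoint is death within 40 days, and the protocol stops observing patients at several points before then. One of those points, ICU need, marks patients whose prognosis is poor. If that rule is followed, the outcome in intubated patients may not be observable at all.

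The SAP lengthens follow-up but opens a second gap through Item 24a. The log-rank test assumes that censoring is unrelated to prognosis. Patients who react to the supplement, or take too little of it (Item 19a sets adherence above 95%), can arise mainly in the IG. ICU admission, treatment failure and oral intolerance can arise in both arms. Followed as written, the rules allow censoring that depends on both arm and prognosis, and the direction of any bias cannot be known beforehand.

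The two start dates for ventilated-patient mortality are a smaller matter. They define different survival times for the same patients.

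**Working it through.** **1. The rules side by side.**

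| Event | Rule as written | What the primary outcomes need |
|---|---|---|
| ICU need or admission | Protocol: participation ends | Status to day 40, including after intubation |
| Discharge for improvement | Protocol: follow-up ends | Status to day 40 |
| Day 21 | Protocol: follow-up ends | Status on days 22 to 40 |
| Treatment failure, oral intolerance, compromising reactions | Protocol: elimination | Status to day 40 |
| Withdrawal from intervention; reactions or poor adherence | SAP Item 24a: follow-up stops or patient leaves | Status to day 40 |

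A ward death before any exit and before day 21 is observed under both documents.

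**2. Reproducing the reported p value.** Inputs (Figure 2 legend): 7/40 control group (CG) deaths, 1/40 IG deaths, log-rank p = 0.027. At each death E = n_CG/n and V = n_CG × n_IG/n²; chi-square = (O − ΣE)²/ΣV on 1 df. With no ties and no censoring before the last death, the eight possible positions of the IG death give chi-square 4.79 to 5.09 and two-sided p 0.029 to 0.024. The reported 0.027 lies inside, so it is a two-sided value.

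**3. Scale of the ICU rule.** Ventilated deaths (Figure 3 legend): 5 of 7 CG, 1 of 3 IG, so 6 of all 8. Non-ventilated deaths: 7 − 5 = 2 CG and 1 − 1 = 0 IG.

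- If none of the six had left through the ICU rule before dying, 7 v 1 is observed.
- If all six had, 2 v 0 is observed. Log-rank:
  - ventilated patients still at risk at both deaths: ΣE = 40/80 + 39/79 = 0.9937, ΣV = 0.49996, chi-square = (2 − 0.9937)²/0.49996 = 2.03, two-sided p = 0.15;
  - ventilated patients (7 and 3) censored first: ΣE = 33/70 + 32/69 = 0.9352, ΣV = 0.49787, chi-square = 2.28, two-sided p = 0.13.
- Fisher's test on 2/40 v 0/40 gives 2 × 780/3160 = 0.49, but it counts eliminated patients as survivors. The SAP's test is the log-rank.

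This range concerns only the ICU exit of ventilated patients. It takes the two other CG deaths as observed and does not model censoring at discharge or day 21.

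**4. What the reported results show.**

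- Survival of 82.5% and 97.5% equals 33/40 and 39/40.
- One IG death at day 12.4 gives a mean of (39 × 40 + 12.4)/40 = 39.31, as reported. With no earlier censoring the 95% CI is 37.97 to 40.65, against 37.98 to 40.64 reported. This is silent on censoring after that death.
- Table 2-A excludes the deceased, leaving 33 CG and 39 IG survivors. Saturation is recorded for 28 and 38, home-oxygen need for 27 and 39. Survivors with no day-40 item therefore number at most min(33 − 28, 33 − 27) = 5 in the CG and min(39 − 38, 39 − 39) = 0 in the IG. This holds if home-oxygen need was recorded at day 40; Item 15 links home-oxygen use to discharge.

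**The case against.** The best defence is that the SAP already supplies the longer follow-up and does not repeat the ICU exit. Ventilated deaths are reported, so that exit did not remove those patients. The Figure 2 legend describes 40-day follow-up as completed, and the survival percentages are exact fractions of 40. Items 24b, 24c and 19d promise the timing and reasons of withdrawals and losses, and deviations by group. The CONSORT and Kaplan-Meier figures, not reproduced in the text reviewed, may show attrition. Item 20 analyses both groups and Item 24a keeps leavers' data, so no general exclusion is planned.

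All of this stands, and it limits the point. It does not reconcile the documents, and it provides no vital status for patients who leave under Item 24a. On Item 20 only explicit wording is missing.

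A reader might go further in three ways that the documents do not support.

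- **The ICU rule would leave 2 v 0.** That needs every ventilated patient who died to have entered the ICU. The documents do not say so, and the protocol's non-inclusion criteria list ventilatory support and ICU admission separately.
- **One unseen IG death could undo the result.** Table 2-A has a home-oxygen entry for all 39 IG survivors, so it shows no IG survivor without a record, subject to the caveat on timing.
- **Fewer CG day-40 records mean unequal loss of deaths.** A missing item is not unknown vital status.

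**Conclusion.** The point holds as a contradiction between protocol and SAP on when observation ends, with a separate gap in Item 24a and two start dates for ventilated-patient mortality. It needs correcting because it decides whether the primary endpoint can be observed as defined. The case rests on the text. The range in step 3 only shows how much could depend on which rule governs.

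A reader might infer that the reported survival difference is biased. The documents do not show this: no mortality loss is visible, the number of Item 24a leavers is not given, and the direction of any effect is open. What remains unsettled is which follow-up rule was applied, to whom, and whether vital status at day 40 is known for everyone.

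**What to change.** Reconcile protocol section 8.4 (both parts) with SAP Items 14, 15, 24a and 26a, without changing any clinical or treatment-stopping rule.

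- Add to both documents: *Whatever happens to study treatment, every randomised patient is followed for vital status and intubation to day 40 from randomisation, unless consent to follow-up is withdrawn, and is analysed in the arm assigned.*
- Amend Item 24a points 1 and 4 to match, so that leaving the intervention does not end vital-status follow-up.
- State one start date for ventilated-patient mortality in Items 14, 15 and 26a.
- Because results are already in the SAP, report by arm which follow-up rule was applied, how many patients left under Item 24a or the elimination criteria, and how many have unknown vital status at day 40.

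The cost is wording, plus a chart or phone check of vital status within contact the SAP already plans. No patients are added and care does not change.

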8.4 Procedure

Once the participants have been selected, the patients and/or family members will be interviewed to explain the protocol and to obtain the signatures of the informed consent letters (Annex 1). Confirmatory test for COVID-19 by PCR, which should confirm the diagnosis in order for the study to continue. Complete clinical and dietary history. Complete blood count: leukocytes, neutrophils, eosinophils, basophils, lymphocytes, monocytes, erythrocytes, red blood cell count, hemoglobin, hematocrit, mean corpuscular volume (MCV), mean hemoglobin concentration (MHC), mean corpuscular hemoglobin concentration (MCHC), platelets and mean platelet volume (MPV). 4. Blood chemistry (glucose, urea, urea nitrogen (BUN), creatinine, BUN/creatinine ratio, uric acid, calcium, phosphorus, sodium, potassium, chloride, magnesium, glomerular filtration rate (GFR), triglycerides, total cholesterol, low density lipoproteins (LDL), high density lipoprotein (HDL), very low density lipoprotein (VLDL), total lipids, total, direct and indirect bilirubin, alanine aminotransferase (ALT), aspartate aminotransferase (AST), gamma glutamyl transpeptidase (GGT), lactate dehydrogenase (LDH), total proteins and albumin. 5. D-dimer (see section 2.3.6). 6.

Coagulation times, bleeding time and prothrombin time. (See section 2.3.6). 7. Fibrinogen. (Serum electrolytes: sodium, potassium, magnesium, and chlorine. (See section 2.3.7 and 2.3.8). 9. Serum homocysteine levels. (See section 2.3.3). Serum levels of 25 hydroxycholecalciferol. (See section 2.6). 11. Taking of tricipital fold and arm circumference, % muscle mass, % fat, BMI, weight, height. 12. Assignment to the research group in a random way, which will have the following characteristics: A) QA: calculate the Basal Energy Expenditure (BEE) per 1.5 of stress factor by means of the Harris Benedict equation. The distribution of macronutrients will be 50% for carbohydrates, 30% for lipids and 20% for proteins. The food will be established according to what is established in the nutrition department of the Centro Médico ISSEMYM Toluca Arturo Montiel Rojas. B) GI: calculate the Basal Energy Expenditure (BEE) plus the stress factor using the Harris Benedict equation. The distribution of macronutrients will be 50% for carbohydrates, 30% for lipids and 20% for proteins. The food will be established according to what is established in the nutrition department of the Centro Médico ISSEMYM Toluca Arturo Montiel Rojas, together with the following supplementation: 1. Neurobion injectable solution of 10 mg, 1 every 24 hrs for 5 days IM. 2. One sachet of NSS-1 in the morning and one sachet in the afternoon mixed with 400 ml of water each, containing: Spirulina Maxima 2. 5 g, folic acid 5 mg, Glutamine 5g, Cyanomax Ultra (10 grams of powder), ascorbic acid 1 g, zinc 20 mg, selenium 100 mcg, cholecalciferol 2000 IU, resveratrol 200 mg, concentrated omega 3 fatty acids (10 grams of powder), L-Arginine 1.5 g, and magnesium 400 mg. During the entire procedure. 3. 500 mg of *Saccharomyces Bourllardii*, administered with 1 capsule of 250 mg during breakfast and lunch, for the first 6 days.

The energy balance of the supplements will be considered within the designated caloric balance for this group. The follow-up will be performed daily for 21 days or earlier, if they are discharged from hospital due to improvement in evolution or require access to the ICU, at which time the patient concludes the study. The following points will be supervised: 1. Application and consumption of the NSS supplementation as appropriate. 2. Recording of all the information in the records. 3. Food diaries of each patient. 4. Laboratory studies: QS every other day, BH every 3rd day, coagulation times every 3rd day, D-dimer and fibrinogen every 3rd day, serum electrolytes every other day, serum homocysteine every other day and serum 25 hydroxycholecalciferol levels every other day. 5. SpO2 %, heart rate, respiratory rate. 6. Clinical evaluation and record of bowel movements. 7. Taking of tricipital fold and arm

circumference, % muscle mass, % fat, BMI, weight, height every two days. 8. Days of hospital stay.

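### The protocol's exit rules and SAP Item 24a end follow-up at events that predict death, while the SAP's primary survival analysis needs vital status to day 40; survival in intubated patients is a post-randomisation subgroup and should not be primary

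*Protocol*

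**What the plan says.** **Protocol.** Section 8.4 (Inclusion and exclusion criteria) reads: "Criteria for elimination: 1. Treatment failure. 2. Admission to ICU for any reason. 3. Patients who do not tolerate the oral route". A fourth criterion is "Reactions to treatment that compromise the health of the patients". Section 8.4 (Procedure) fixes the length of follow-up: "The follow-up will be performed daily for 21 days or earlier, if they are discharged from hospital due to improvement in evolution", or if they "require access to the ICU, at which time the patient concludes the study". It does not say whether an eliminated patient is censored or dropped.

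**SAP, follow-up.** Item 14 states: "Analysis of overall survival and mortality will be performed from baseline to day 40 or patient death". Items 14 and 15 follow ventilated patients from intubation to day 40 or death. Items 26a and 27 list survival in intubated patients as a primary outcome, tested by log-rank. Item 8 places mortality in intubated patients under secondary objective 1, and Item 26a times it from baseline.

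**SAP, leaving the study.** Item 24a point 1: "Participants can withdraw from the intervention and follow-up stops but the information collected is considered as data". Under point 4, a patient who has a reaction or "does not adequately follow the treatment, they should leave the study and their data will be considered for the analysis". Point 5: "Data from patients who die will be considered in the analysis". Item 20 says that both groups of the 80 patients are analysed for survival, but not that patients who exit stay in the analysis by assigned group. Item 28 plans no method for missing data.

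**The concern.** The log-rank test and the Kaplan-Meier curve assume that a patient who leaves follow-up has the same prospects as those who remain. Patients who need intensive care, cannot take food by mouth or are failing treatment do not. Ending follow-up there removes the patients most likely to die just before they die, and so overstates survival. If such exits are unequal between groups, the comparison is distorted too.

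Item 24a carries a similar risk. Adherence in Item 19a includes taking more than 95% of the NSS, which only the intervention group (IG) receives, so that part of the rule can remove only IG patients. Point 5 keeps the data of patients who die, but no text says that deaths are sought after a patient has left.

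The headline mortality result is at stake: most reported deaths followed ventilation, so it depends on whether those patients stay at risk. The intubated comparison has a separate problem. Being intubated is itself an outcome that treatment could affect, so the two intubated subgroups are no longer comparable by randomisation.

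**Working it through.** **Inputs (SAP, legends to Figures 2 and 3).** Deaths: control group (CG) 7 of 40, IG 1 of 40. Ventilated: CG 7, IG 3. Deaths among the ventilated: CG 5 of 7, IG 1 of 3. Reported log-rank p = 0.027. P-values below are two-sided, because that is what reproduces the reported figure.

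**1. Reported log-rank.** With 40 per group, no censoring before day 40 (assumed) and no tied deaths, the statistic depends only on where the single IG death falls among the eight. Summing n(CG)/n for expected CG deaths E and n(CG)·n(IG)/n² for variance V:
- IG death third of eight: E = 3.880, V = 1.997, χ² = (7 − 3.880)²/1.997 = 4.87, p = 0.027.
- Over all eight positions, p runs from 0.024 to 0.029.

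The reported value therefore fits full follow-up of 7 v 1 deaths.

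**2. Is exit at ventilation prognostic?** Ventilated: 6/10 died (60%). Not ventilated: (8 − 6)/(80 − 10) = 2/70 (2.9%). Fisher p = 0.00002. Ventilation was also uneven, 7 v 3.

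**3. Applying the exit rule at ventilation.** Assume that all ten ventilated patients exit then, and that the remaining deaths come later. Deaths left: CG 7 − 5 = 2, IG 1 − 1 = 0. At risk at those deaths: 33 v 37, then 32 v 37.
- E = 33/70 + 32/69 = 0.935
- V = (33·37)/70² + (32·37)/69² = 0.498
- χ² = (2 − 0.935)²/0.498 = 2.28, p = 0.13
- Day-40 survival: CG 82.5% becomes 31/33 = 93.9%; IG 97.5% becomes 100%.

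If the ten were dropped instead of censored, 2/33 v 0/37 gives Fisher p = 0.22. Either way there would be no follow-up for survival in intubated patients.

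**4. Intubated subgroup.** CG 5/7 = 71.4% (exact 95% CI 29.0 to 96.3); IG 1/3 = 33.3% (0.8 to 90.6). Difference 38.1 points, Newcombe 95% CI −20 to 72, Fisher p = 0.50.

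**5. Which clock does Figure 3-B use?** For one death at time t among n = 3, with the others followed to T (no earlier censoring assumed), the mean is t + a and SE = a/√(n(n − 1)), where a = (2/3)(T − t). The IG mean is 26.66 (11.73 to 41.6).
- SE = (41.6 − 11.73)/3.92 = 7.62; a = 7.62 × √6 = 18.66
- t = 26.66 − 18.66 = 8.0; T = 8.0 + 1.5 × 18.66 = 36.0

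The same method on the Figure 2 IG values (39.31; 37.98 to 40.64) gives the IG death at day 12.5 and a 40.0-day horizon from baseline. That death is the one in Figure 3-B. Timed from baseline (t = 12.5, T = 40), Figure 3-B would show 30.83 (16.16 to 45.50), which it does not. The values are consistent with timing from intubation, as in Items 14 and 15, and not with Item 26a.

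**The case against.** The strongest reply is that the feared censoring did not happen. The SAP reports deaths after ventilation in both groups, the Figure 2 legend describes completed 40-day follow-up with 40 per group, and step 1 shows that the reported p-value fits full follow-up. This stands. A reader might infer from the exit rules that the published curves are biased; the documents do not support that.

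Second, nothing equates ventilation with ICU need or loss of the oral route. The protocol lists ventilatory support and ICU admission as separate non-inclusion criteria. This also stands, so step 3 is conditional. A reader might also be tempted by a Fisher test on 2/40 v 0/40 (p = 0.49). It overstates the shift, because it counts the ten censored patients as survivors and is not the planned test. The like-for-like change is about 0.027 to about 0.13.

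Third, no Item 24a exit is counted anywhere, and Item 24b already asks for withdrawals and their timing to be shown. That rule could remove IG patients selectively, but no evidence shows that it did, and no number can be attached to it.

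Fourth, Item 20 does name 80 patients in two groups. It lacks only the statement that patients stay in the analysis after exit.

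Fifth, the back-calculation uses rounded limits and assumes no early censoring, so it supports the intubation clock without proving it.

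None of this reconciles the texts. The day-21 and discharge limits alone conflict with day 40, whatever ventilation implies about ICU need.

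**Conclusion.** The point holds as a conflict between documents. The protocol exits and Item 24a(1) and (4), applied as written, would censor survival at a strongly prognostic event (60% v 2.9% mortality) and would leave one listed primary outcome without follow-up. The analysis appears to have followed the SAP, which is the less biased course. In the text available, neither document acknowledges that this departs from the protocol or states it as a rule for all randomised patients.

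The size is conditional. If all ten ventilated patients had exited at ventilation, with the other two deaths occurring later, deaths would be 2 v 0 and log-rank p about 0.13. If only some had met an exit criterion, the effect would be smaller by an amount the documents do not allow one to calculate.

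The subgroup point does not depend on this. Survival in intubated patients compares 7 with 3 patients selected after randomisation, has an interval from −20 to 72 points, is primary in Items 26a and 27 but secondary in Item 8, and has two time origins. It does not support the 38.1% reduction given in the Figure 3 legend as an effect of the NSS. This should be corrected, but it does not by itself overturn the overall survival comparison.

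**What to change.** 1. In both protocol 8.4 sections and SAP Item 24a(1) and (4), state that meeting an exit criterion or stopping treatment does not end follow-up. Ventilation and vital status are collected to day 40 from baseline unless the patient withdraws consent to follow-up. Day 21 or discharge ends daily monitoring only. Add no new rule for stopping treatment; report actual NSS exposure from the Item 19b daily records.
2. In Items 20 and 27, state that the primary log-rank includes all 80 randomised patients by assigned group, at risk until death or day 40 from baseline. Check day-40 vital status for anyone who stopped treatment or was eliminated.
3. Make survival in intubated patients descriptive, with 5/7 and 1/3, exact intervals and one clock from intubation (correct Item 26a). Drop the 38.1% reduction as an NSS effect and align Item 8.
4. Results to April 2021 already stand in the SAP, so label these edits as made after results and report the departure from the protocol's follow-up and elimination rules.

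The cost is one text amendment, a vital-status check and a review of NSS records for the ten ventilated patients. No new patients are needed. The claim of benefit in intubated patients is lost.
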